Nivolumab Administration	Nivol begin at 6 n	lumab v ming on ng/kg Q	vill be a n Cycle 14W up	Nivolumab will be administered on a 480 mg Q4W schedule beginning on Cycle 1 Day 1. Adolescent doses will be administered at 6 mg/kg Q4W up to a maximum of 480 mg. Refer to Section 4	ered on . Adoles «imum (a 480 m scent do of 480 n	ng Q4W ses will ng. Refe	schedu be adr r to See	ale ainistere ction 4	pe		For subjects assigned to combination therapy only.
Abbreviations: CRPC = castrate resistant prostate canc PSA = prostate specific antigen; Q2W = every 2 weeks	castrate ntigen;	: resistal Q2W =	nt prost = every 2	ate canc 2 weeks	er; D =	Day; E	OT = E	nd of tı	reatmen	ıt; FDC	J-PET =	Abbreviations: CRPC = castrate resistant prostate cancer; $D = Day$; $EOT = End$ of treatment; FDG - $PET = fluorodeoxyglucose - positron emission tomography; PSA = prostate specific antigen; Q2W = every 2 weeks$
^a Refer to Table 5.1-6 for Clinical Follow-up and Survival Follow up Periods	or Clinic	cal Foll	ow-up a	und Surv	ival Fol	llow up	Periods					
^b QTcF assessments ≥450 msec must be confirmed on repeat EC matched ECGs will also occur on specific days and time points.	50 msec	: must b r on spe	e confi cific da	rmed on iys and t	repeat ime poi	ECG. E nts.	CGs sho	ould be	recorde	ed after	the sub	QTcF assessments >450 msec must be confirmed on repeat ECG. ECGs should be recorded after the subject has been supine for at least 5 minutes. Serial time matched ECGs will also occur on specific days and time points.
^c ECG collection instruc	tions. F	or mon	otheran	w treatm	ent FC	Ge are ti	lloo ed o	lerted a	ut all tim	nenoint	s indicat	ECG collection instructions. For monotherany treatment ECGs are to be collected at all timenoints indicated in Table 5.5.1-4. For combination

- ^c ECG collection instructions: For monotherapy treatment ECGs are to be collected at all timepoints indicated in Table 5.1-5 and Table 5.5.1-4. For combination therapy treatment ECGs are to be collected at timepoints indicated in Table 5.1-5 only
 - d For cycle 1 only, assessments may be performed up to 72 hours prior to dosing

Clinical Protocol BMS-986158 BET Ir	CA011001 BET Inhibitor
^e Thyroid function testing only required for Part 2 Combination treatment with Nivolumab	
^g Contrast enhanced CT of the chest, CT/MRI of the abdomen, pelvis, and all other known and/or suspected sites of disease. FDG-PET for hematologic malignancies. See Section 5.3.1 for further details. Bone scan for prostate cancer. Note: Patients who crossover from monotherapy to combination therapy will begin at Cycle 1.	atologic
Revised Protocol No.: 07 Date: 18-Mar-2019	125

	Clinical Follow-up	Clinical Follow-up	Clinical Follow-up	Survival Follow-up	
Procedure	30 days (+/- 5 days)	60 days ^a (+/- 5 days)	100 days ^a (+/- 5 days)	every 12 weeks (+/- 2 weeks)	Notes
Safety Assessments					
Physical Examination (PE)	X	Х	X		See Screening notes. Include breast exam if clinically indicated.
Vital Signs	х	Х	Х		Includes body temperature, blood pressure and heart rate
Performance Status (ECOG)	Х	Х	х		ECOG score (se Appendix 5)
Laboratory Tests	Х	Х	Х		See Section 5.3.2 on "Hematology" and "Serum Chemistry" for specific tests to be included.
Thyroid Function Tests ^b	х	Х	Х		To include TSH with reflex testing (free T3 and free T4) if TSH is abnormal b
PSA for CRCP subjects only	Х	Х	х	Х	
Tumor Assessment				X	For the first year of survival follow-up for subjects who do not already have PD. For participants with CRPC and NEPC, whole body bone scans should also be performed. For participants with TNBC without measurable lesions
					outside the breast, contrast enhanced MRI of the breasts should also be performed.
Adverse Event Reporting	orting				
Monitor for non- Serious Adverse Events	Х	Х	Х		Non-serious AEs will be collected starting with the first dose of study medication and through 30 days after discontinuation of dosing for subjects receiving BMS-986158 monotherapy,

Clinical Follow-up and Survival Follow-up Phase Procedural Outline (CA011001) **Table 5.1-6:**

	Clinical Follow-up	Clinical Follow-up	Clinical Follow-up	Survival Follow-up	
Procedure	30 days (+/- 5 days)	60 days ^a (+/- 5 days)	100 days ^a (+/- 5 days)	every 12 weeks (+/- 2 weeks)	Notes
					and through 100 days for subjects receiving combination therapy.
Monitor for Serious Adverse Events	Х	Х	Х		All SAEs must be collected starting at the time a subject signs informed consent and through 30 days after discontinuation of dosing for subjects receiving BMS-986158 monotherapy, and through 100 days for subjects receiving combination therapy.
Sample Collection					
Pharmacokinetic (PK) Sampling	Х		X		See Section 5.5.1; For subjects receiving combination therapy only

Clinical Follow-up and Survival Follow-up Phase Procedural Outline (CA011001) **Table 5.1-6:**

_
CA011001)
al Outline (
Procedura
-up Phase
/al Follow-
and Surviv
Follow-up
Clinical
-0:
Table 5.1

	ı					
CAULIUUL)		Notes				
Clinical Follow-up and Survival Follow-up Phase Procedural Outline (CAUTIOUI)	Survival Follow-up	every 12 weeks (+/- 2 weeks)	·			
urvivai follow	Clinical Follow-up	100 days ^a (+/- 5 days)				
c nuo and su contraction of the second se	Clinical Follow-up	60 days ^a (+/- 5 days)	• •			
Clinical FO	Clinical Follow-up	30 days (+/- 5 days)				
1 able 5.1-0:	, , ,	Procedure				

^a Clinical follow-up for patients who receive BMS-986158 in combination with nivolumab will be 60 days and 100 days following the last dose of study drugs ^b Thyroid function testing only required for Part 2 participants Combination treatment with Nivolumab

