In Part 2, Schedule A for BMS-986158 administration has been selected for expansion of the 4.5 mg dose, which will be administered for 2 weeks (10 doses) followed by 3.75 mg for the remainder of the treatment period. Adult and adolescent subjects weighing ≥ 40 kg will be administered a flat dose of BMS-986158 (see Section 1.1.13). Using Schedule A with a loading period of 2 weeks at 4.5 mg followed by 3.75 mg for the remainder of the treatment period, BMS-986158 will be tested as monotherapy, initially in a limited set of tumor types (NMC, CRPC, DHL, Non-DC-DLBCL, and TNBC; Initial Expansion), with Subsequent Expansion into additional tumor types upon observing signals of antitumor activity or favorable PD effects in the initial set of tumor types. If combination therapy is pursued, nivolumab will be administered as a flat dose of 480 mg Q4W in adults and BMS-986158 will be administered using Schedule A.

Further dose modification at the subject level is permitted below the dose level of 3.75 mg depending on the observed toxicity and tolerability (see guidelines for dose modification in Section 4.5.2).

Subjects will complete up to 5 study periods (See Figure 3.1-2): Screening (up to 28 days for Part 1 and up to 40 days for Part 2), Treatment (up to 2 years, until disease progression or other protocolspecified criteria), Clinical Follow-up (30 days for BMS-986158 monotherapy and 30 days, 60 days, and 100 days for combination therapy, if pursued), and Survival Follow-up

Only subjects who

have progressive disease after receiving BMS-986158 in combination with nivolumab may have the option to continue treatment with the combination if combination therapy is pursued. Subjects who have progressive disease after receiving BMS-986158 monotherapy will not have the option to continue treatment with BMS-986158 monotherapy or to receive BMS-986158 in combination with nivolumab.

Revised Protocol No.: 07 Date: 18-Mar-2019

.

[figure not shown]
Safety, PK, and efficacy measurements will occur as indicated in Table 5.1-1, Table 5.1-2 Table 5.1-3, Table 5.1-4, Table 5.1-5, and Table 5.1-6. Pre- and on-treatment biopsies will be required for all adult subjects enrolled in Part 2 to allow the assessment of BMS-986158-induced changes in tumor immune infiltration

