		ndinat	non w		Nolum	Iad Ex	Combination with Nivolumad Expansion - Schedule A	0 - N	cnear	ule A ·	- S day	- 2 days on/2 days off dosing schedule
Procedure	`ٽ	Cycle 1 (28 Days)	28 Day	s)	C	cle 2 (2	Cycle 2 (28 Days)		Cycle 3 and beyond (28 Days)	le 3 ld d (28 vs)	EOT ^a	
± 3 days (for all visits except C1D1 and mandatory tumor biopsy)	D J	8 G	51 A	D 77	I A	8 A	51 A	77 A	D I	51 A		Notes
												* CBC only (±24hours)
Thyroid Function Tests ^e	×				×				×		×	Collect on Day 1 every cycle, predose, beginning with Cycle 1 Day 1 and at EOT. To include TSH with reflex testing (free T3 and free T4) if TSH is abnormal. Results should be examined by the investigator or appropriate designee within 48 hours of dose administration
PSA for CRPC subjects only	Х				Х				Х		Х	Collect on Day 1 every cycle, predose, beginning with Cycle 1 Day 1 and at EOT.
Coagulation Panel	×	×	×	×			X*				*X	aPTT, PT and INR. * Cycle 2 and beyond to be done if clinically indicated (e.g. signs of bleeding, especially GI bleeding). See Section 5.3.2 for details
MUGA/ECHO						Х						Only if clinically indicated with the same assessment used at screening. See notes in screening.
Pregnancy Test	Х				Х				Х		Х	For WOCBP only. Sensitivity of test must be at least 25 IU/L or equivalent units of HCG. Pregnancy test must be done within 24 hours prior to starting study drug
Adverse Event Reporting												

On Treatment & Follow-Up Outline (CA011001)- Part 2 BMS-986158 Monotherapy and/or in Combination with Nicolumet Expansion Schodule A 5 days on/2 days off desing schodule **Table 5.1-5:**

Revised Protocol No.: 07 Date: 18-Mar-2019

121

1 and 2.1-5.	Cor	Combination with	ion w	ith Ni	wolum	ab Ex	pansi	on - S	chedu	l al l	-5 days	Combination with Nivolumab Expansion - Schedule A - 5 days on/2 days off dosing schedule
Procedure	C	Cycle 1 (28 Days)	28 Day	(s	Cy	cle 2 (2	Cycle 2 (28 Days)	()	Cycle 3 and beyond (28 Days)	le 3 d d (28 /s)	EOT ^a	
± 3 days (for all visits except C1D1 and mandatory tumor biopsy)	D I	8 G	SI (I	D 77	I O	8 G	SI (I	D 77	D 1	SI (I		Notes
Monitor for Non- Serious Adverse Events						×						See Section 6.2. Non-serious AE will be collected from first dose of study drug until 30 days post discontinuation of dosing. AEs reported during this time period should be followed until resolved to baseline, stabilized or deemed irreversible

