Monitor for Serious Adverse Events						Х						All SAEs must be collected from the date of subject's written consent until 30 days post discontinuation of dosing or subject's participation in the study if the last scheduled visit occurs at a later time.
Sample Collection												
Pharmacokinetic (PK) Sampling					X							See Section 5.5. Patients who crossover from monotherapy to combination therapy will not be required to provide samples for PK.
Efficacy Assessments												
Tumor Assessments ^g					Х						X*	Turnor Assessments should occur every 8 weeks $(\pm 7 \text{ days})$ from date of first dose until PD or treatment discontinuation, whichever occurs later.

On Treatment & Follow-Up Outline (CA011001)- Part 2 BMS-986158 Monotherapy and/or in **Table 5.1-5:**

On 1 reatment & Follow-Up Outline (CAULIUUL)- Fart 2 BMS-980138 Monotherapy and/or in Combination with Nivolumab Expansion - Schedule A - 5 days on/2 days off dosing schedule		Notes	For participants with CRPC and NEPC, whole body bone scans should also be performed. For participants with TNBC without measurable lesions outside the breast, contrast enhanced MRI of the breasts should also be performed. *EOT if not assessed within the last 9 weeks.
- 5 day	EOT ^a		
lule A	Cycle 3 and beyond (28 Days)	SI (I	
Sched	Cyc ai beyoi Da	1 0	
sion -	(sá	D 22	
Expan	(28 Da	SI (I	
mab F	Cycle 2 (28 Days)	8 G	
Vivolu		1 0	
with N	(sti	D 77	
ation	Cycle 1 (28 Days)	SI (1	
mbin	Cycle 1	8 U	
Combination with 1		1 U	
	Procedure	± 3 days (for all visits except C1D1 and mandatory tumor biopsy)	

nical Protocol	[S-986158
Clinic	BMS-

Table 5.1-5:	On Coi	Treat mbina	tment tion w	& Foll /ith Nř	low-U _l volum	p Outl ab Ex	ine (C. pansio	A011(n - Sc	001)-] Shedul	Part 2 le A -	t BMS- 5 days	On Treatment & Follow-Up Outline (CA011001)- Part 2 BMS-986158 Monotherapy and/or in Combination with Nivolumab Expansion - Schedule A - 5 days on/2 days off dosing schedule
Procedure		ycle 1 (Cycle 1 (28 Days)	(s/	Cy	cle 2 (2	Cycle 2 (28 Days)		Cycle 3 and beyond (28 Days)		EOT ^a	
± 3 days (for all visits except C1D1 and mandatory tumor biopsy)	1 0	8 G	D 12	D 77	I O	D 8	51 A	D 77	D I	SI (1		Notes
Clinical Drug Supplies												
BMS 986158 Administration		Dosing	regimei	Dosing regimen is 5 days on, 2 days off. Refer to Section 4	ys on, 2	days o	ff. Refei	to Sec	tion 4			Those supplied by BMS or sourced by the investigator. Refer to Section 4

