5.3 Safety Assessments

All subjects who receive at least one dose of BMS-986158 will be evaluated for safety parameters. Additionally, any occurrence of an SAE from the time of consent until 30 days post discontinuation of BMS-986158 monotherapy and 100 days post discontinuation of combination therapy will be documented. Any occurrence of non-serious AEs will be collected from first dose of study drug until 30 days post discontinuation of BMS-986158 monotherapy and 100 days post discontinuation of combination therapy. AEs will be coded using the most current version of MedDRA. Safety will be evaluated for all treated subjects using the NCI CTCAE v4.03. Safety assessments will be based on medical review of AE reports and the results of vital sign measurements (body temperature, respiratory rate, heart rate, and blood pressure (heart rate and blood pressure should

be measured after subject has been resting quietly for at least 5 minutes), physical examinations and clinical laboratory tests. Subjects should be followed until all AEs for which no clear alternative cause is identified other than to BMS-986158 have recovered to baseline or are deemed irreversible by the investigator. The incidence of AEs will be tabulated and reviewed for potential significance and clinical importance.

The schedule of required visits, tests, procedures and assessments are described Table 5.1-1, Table 5.1-2 Table 5.1-3, Table 5.1-4, Table 5.1-5, and Table 5.1-6.

In limited instances, scheduled events (including events other than safety assessments) can occur outside of the indicated timeframes but the Sponsor should first be notified.

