6.2.1 Nonserious Adverse Event Collection and Reporting

The collection of nonserious AE information should begin at initiation of study drug until the time points specified in the Schedule of Activities (Section 5). Nonserious AE information should also be collected from the start of the screening period or other observational period intended to establish a baseline status for the subjects.

Nonserious AEs should be followed to resolution or stabilization, or reported as SAEs if they become serious (see Section 6.1.1). Follow-up is also required for nonserious AEs that cause interruption or discontinuation of study drug and for those present at the end of study treatment as appropriate. All identified nonserious AEs must be recorded and described on the nonserious AE page of the CRF (paper or electronic).

Completion of supplemental CRFs may be requested for AEs and/or laboratory abnormalities that are reported/identified during the course of the study.

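### Table 5.1-5 gives one 30-day window for non-serious AEs with no split by regimen, while other sections set 100 days for combination subjects, so 0 to 70 days of new-onset non-serious AEs could go uncollected if the combination is pursued

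*Protocol*

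**What the plan says.** Table 5.1-5 (Protocol Section 5.1) is the Part 2 schedule for monotherapy and/or combination. It includes a nivolumab administration row marked "For subjects assigned to combination therapy only", so combination subjects are plainly within it.

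- **Non-serious AEs, Table 5.1-5:** "Non-serious AE will be collected from first dose of study drug until 30 days post discontinuation of dosing". The row does not distinguish regimens and cross-refers to Section 6.2.
- **SAEs, Table 5.1-5:** "All SAEs must be collected from the date of subject's written consent until 30 days post discontinuation of dosing". The row extends this if the last scheduled visit falls later.
- **Section 5.3:** AEs are collected "until 30 days post discontinuation of BMS-986158 monotherapy and 100 days post discontinuation of combination therapy".
- **Table 5.1-6 (follow-up schedule):** 30 days for monotherapy, "and through 100 days for subjects receiving combination therapy".
- **Section 6.1.1:** SAEs within 100 days of discontinuation for combination.
- **Section 6.2.1:** non-serious AEs run "until the time points specified in the Schedule of Activities (Section 5"; it gives no number of its own.
- **Section 8.3.1 and the synopsis:** the primary safety endpoints are evaluated for up to 100 days after the last combination dose.

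On follow-up visits, one paragraph of Section 3.1 gives "30 days, 60 days, and 100 days for combination therapy, if pursued". The synopsis, a later paragraph of Section 3.1 and footnote a of Table 5.1-6 name only the last two; the footnote says follow-up "in combination with nivolumab will be 60 days and 100 days following the last dose of study drugs".

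**The concern.** The combination's primary objective is safety and tolerability, and AE incidence is one of its primary endpoints. An event not recorded at the time may not be recoverable later. If some sites stop recording non-serious AEs at day 30 and others continue to day 100, the combination AE tables mix two observation windows, and the shortfall depends on site practice.

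The text does not settle the matter by itself. The Table 5.1-5 row points to Section 6.2, and Section 6.2.1 points back to the Section 5 schedule, where Tables 5.1-5 and 5.1-6 differ. The 30-day wording also appears in the Part 1 tables, where it is right because Part 1 is monotherapy only. Table 5.1-5 still carries notes about crossover to combination, which Sections 3.1 and 3.1.2.4 no longer allow. Both facts suggest wording that was not updated, rather than a deliberate shorter window.

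**Working it through.** The plan states no figure to reproduce, and no power or error rate is involved. The check compares the stated windows.

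| Source in the protocol | Non-serious AEs, combination | SAEs, combination |
|---|---|---|
| Table 5.1-1 | not stated | 100 days |
| Table 5.1-5 | 30 days (no split) | 30 days, or later if the last scheduled visit is later |
| Table 5.1-6 | 100 days | 100 days |
| Section 5.3 | 100 days | 100 days |
| Section 6.1.1 | not applicable | 100 days |
| Section 6.2.1 | defers to Section 5 | not applicable |

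Section 8.3.1 evaluates safety over 100 days for combination.

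**Days at stake.** A site that applies Table 5.1-5 literally loses 100 − 30 = 70 days (days 31 to 100), which is 70/100 = 70% of the post-treatment window. A site that follows Table 5.1-6 or Section 5.3 loses 0. The range is 0 to 70 days. This is a share of days, not of events.

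**Subjects at stake.** Table 3.1.2.4-1 plans up to 14 × 9 = 126 combination subjects. The 6 to 12 subjects in the combination safety evaluation are the first treated across those cohorts (Section 3.1.2.2), so they are inside the 126. A further 6 to 12 are added only if a lower dose must be evaluated: 126 + 12 = 138 at most.

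**Endpoint components at stake (Section 8.3.1).**
- New-onset non-serious AEs after day 30: exposed.
- Non-serious AEs already reported: followed to resolution, stabilisation or irreversibility under the same row.
- SAEs: 100 days in four places, and the Table 5.1-5 row extends to a later last visit.
- Deaths: captured as SAEs.
- AEs leading to discontinuation: they arise before the post-treatment window.
- Laboratory shifts: tests are scheduled at days 30, 60 and 100 in Table 5.1-6.

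**Effect on any-AE incidence.** In Part 1, 79 of 81 subjects (97.5%) had at least one AE (Section 1.4.4). Assume the combination has at least that incidence by day 30. Then at most 100 − 97.5 = 2.5 percentage points of any-AE incidence could be lost. That bound does not apply to individual event terms or to worst grade, for which the documents give no basis for an estimate.

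**Effect on exposure-adjusted rates.** SAP Section 8.2 defines exposure for combination subjects followed at least 100 days as (last dose date − first dose date) + 100 + 1. With d = last − first in days, the fraction of the denominator with no non-serious collection under a 30-day stop is 70/(d + 101). Taking d as an assumption: two 28-day cycles (d = 56) give 70/157 = 44.6%, and the two-year treatment maximum (d = 730) gives 70/831 = 8.4%. The rate would be biased downward by an amount that depends on when events occur.

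**The case against.** The best answer is that the protocol already tells sites what to do after treatment. Footnote a on the end-of-treatment column of Table 5.1-5 refers to Table 5.1-6 for follow-up. That table marks non-serious AE monitoring at days 30, 60 and 100 and states 100 days for combination. Section 5.3, which is part of the Section 5 that Section 6.2.1 invokes, gives the same split explicitly, and the synopsis and Section 8.3.1 agree. On this view one unsplit note stands against a consistent rule.

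Most of this stands, and it is why the lower end of the range is zero. It does not remove the contradiction. The footnote is attached to the end-of-treatment column rather than to the AE row, the table's title covers follow-up as well as treatment, and the row states its own stop date. A site that stops at day 30 would be obeying a protocol table.

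Three stronger readings are tempting, and the documents do not support them:
- **The primary safety endpoint as a whole loses 70 of its 100 days.** Its other components are largely protected, as set out in the component list.
- **Sites will in fact stop at day 30.** That requires them to pass over the footnote and the AE rows at the day-60 and day-100 visits. It is possible, not established.
- **The combination visit schedule is itself in conflict.** In the Table 5.1-6 grid, footnote a is attached only to the day-60 and day-100 columns, the day-30 column is unrestricted, and combination-only PK is marked at days 30 and 100. Table 5.5.1-5 also lists a 30-day follow-up. The grid therefore matches 30/60/100, and what remains is loose wording elsewhere.

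It is also fair that no current analysis is affected. The combination is conditional on monotherapy data, and SAP version 2.0 is limited to Part 1 and the Part 2 Initial Expansion.

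**Conclusion.** The contradiction holds and should be corrected. Table 5.1-5 applies to combination subjects yet gives a 30-day stop for non-serious AEs, against 100 days in Sections 5.3 and 8.3.1 and Table 5.1-6. Its SAE row has the same unsplit 30 days, softened by the later-visit clause, against 100 days in Section 6.1.1.

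The loss is 0 to 70 days per combination subject. It is confined mainly to new-onset non-serious AEs in days 31 to 100, in up to 126 subjects (138 with a lower-dose evaluation), and it arises only if the combination is pursued. The monotherapy window is 30 days throughout. The upper end assumes a site applies Table 5.1-5 literally. Any effect on exposure-adjusted rates assumes that a future combination analysis adopts the SAP Section 8.2 denominator. This is an internal inconsistency with a clear intended rule, not a flaw in the design.

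**What to change.** - In Table 5.1-5, reword both AE rows to 30 days after discontinuation of monotherapy and 100 days after discontinuation of combination therapy, in line with Sections 5.3, 6.1.1 and 8.3.1 and Table 5.1-6.
- Align the combination follow-up visit wording in the synopsis, both places in Section 3.1 and footnote a of Table 5.1-6 with the Table 5.1-6 grid (30, 60 and 100 days).

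Make both changes before any combination cohort opens. They need no added visits, subjects or analyses: the cost is wording in the next amendment.
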